### **8.4.3. 12-Lead Electrocardiograms**

12-Lead electrocardiograms (ECGs) will be performed during Screening, pre-dose on Day 90, and on Day 180. Any clinically significant abnormalities are to be recorded. The ECG recording will be printed, and the Investigator or delegated staff will initial and date the printout to indicate

their review of the findings. The trace and the interpretation will then be stored with the Participant's records.

#### **8.4.4. Ultrasound of Right and Left Lower Legs**

A posterior-to-anterior (P-A) ultrasound of the right and left lower extremities will be performed at Screening to assess the surface area and depth of skin, subcutaneous tissue, and fat covering the gastrocnemius muscles of each leg and the location of other anatomical components that might interfere with the Engensis Injections.

- The surface area of the gastrocnemius muscle available for placement of the 16 injections of Engensis (which must be injected into skeletal muscle to be effective) will be calculated by multiplying the length (medial and lateral condyles of the femur to the top of the Achilles tendon/gastrocnemius aponeurosis) and the width (widest section that includes the medial and lateral heads of the gastrocnemius muscle) identified by ultrasound.
- The depth of the skin and subcutaneous tissue to the surface of the gastrocnemius muscle as well as the thickness of the gastrocnemius measured by ultrasound will be used to determine the length of needle that will need to be used for accurate injection of Engensis into the skeletal muscle tissue (to a depth of at least 1 cm into the muscle).
- The location(s) of the Achilles tendon/gastrocnemius aponeurosis and other sites of fibrous tissue or connective tissue within the medial and lateral heads of the gastrocnemius muscle of each leg will be identified by ultrasound. Engensis must not be injected into connective tissue, fibrous tissue, or tendons as HGF cannot be expressed from the plasmid in these tissues.

#### **8.4.5. Vital Signs**

Vital signs will be measured at Screening, pre- and post-dose at Study Injection Visits during Treatment Cycle 1 (Days 0 and 14) and Treatment Cycle 2 (Days 90 and 104), and at all other Study Visits. Weight will be collected pre-dose at Study Injection Visits. After resting in the seated position for 5 minutes, vital signs measured will include temperature, sitting blood pressure, heart rate, respiratory rate, and oxygen saturation on room air. The method of temperature measurement should be according to the Site's policy and should be consistently applied.

#### **8.4.6. Clinical Laboratory Assessments**

See Section 1.3 (SoA) for the timing and frequency.

The Investigator must review the laboratory report, document this review, and record any clinically relevant changes occurring during the study. The laboratory reports must be filed with the source documents. Clinically significant abnormal laboratory findings are those that are not associated with the underlying disease, unless judged by the Investigator to be more severe than expected for the Participant's condition.

All protocol-required laboratory assessments must be performed in accordance with the

laboratory manual and the SoA.

#### **8.4.6.1. Local and Central Laboratory Assessments**

The following laboratory assessments for safety and establishing eligibility will be performed at local laboratories during Screening as noted in the SoA. Everything from Day 0 to 180 will be performed by the central laboratory.

The Investigator must review the laboratory report, document this review, and record any clinically relevant changes occurring during the study. The laboratory reports must be filed with the source documents and uploaded into the EDC. Clinically significant abnormal laboratory findings are those that are not associated with the underlying disease, unless judged by the Investigator to be more severe than expected for the Participant's condition.

All protocol-required laboratory assessments must be performed in accordance with the laboratory manual and the SoA.

##### **8.4.6.1.1. Hematology**

- White blood cell count
- Neutrophil (including calculated absolute neutrophil count)
- Hemoglobin
- Hematocrit
- Platelet count

##### **8.4.6.1.2. Kidney Function Tests**

- Blood urea nitrogen (BUN)
- Creatinine
- Estimated glomerular filtration rate (eGFR, calculated using the chronic kidney disease epidemiology collaboration [CKD-EPI] formula based on Cystatin C levels)

##### **8.4.6.1.3. Liver Function Tests**

- Aspartate aminotransferase (AST)
- Alanine aminotransferase (ALT)
- Alkaline phosphatase
- Gamma-glutamyl transpeptidase (GGT)
- Total bilirubin
- Total protein
- Albumin

##### **8.4.6.1.4. Clinical Chemistry**

- Electrolytes (sodium, potassium, chloride, bicarbonate, calcium, inorganic phosphate, magnesium)

- Glucose (random collection, i.e., not necessarily fasting)
- Amylase
- Lipase
- Lactate dehydrogenase
- Creatine kinase
- HbA1c
- Cystatin C (for calculation of eGFR)

#### **8.4.6.1.5. Lipid Profile**

- Total cholesterol
- High-density lipoprotein cholesterol (HDL-C)
- Low-density lipoprotein cholesterol (LDL-C)
- Triglycerides

#### **8.4.6.1.6. Additional Tests**

- Urine pregnancy test
- Urine drug analysis

#### **8.4.6.1.7. Viral Screening**

- HIV
- HTLV I/II antibody with reflex confirmatory assay
- HBcAb (IgM)
- HBsAb
- HBsAg
- HBV viral load (if needed clinically)
- Anti-HCV antibodies and a positive qualitative PCR to assess HCV viral load

#### **8.4.6.2. Central Laboratory Analytical Testing**

- Anti-HGF antibodies
- Cytokines

#### **8.4.7. Retinal Fundoscopy**

Proliferative diabetic retinopathy, defined as the presence of new proliferating blood vessels (neovascularization) arising from the retina or optic disc and growing on the retinal surface or into the vitreous cavity, will be assessed by retinal funduscopy during Screening for eligibility and repeated at Day 90 and Day 180/Early Termination. Retinal funduscopy must be performed

by an ophthalmologist or optometrist within 52 days prior to Day 0 and within 45 days of Day 90, and within 30 days of Day 180. The same ophthalmology practice should be used for all measurements of individual participation. In cases where fundoscopy alone is deemed insufficient to determine eligibility, fluorescein angiography may be performed during Screening.

## **8.5. Adverse Events and Serious Adverse Events**

The definitions of AEs, TEAEs, and SAEs can be found in Section 10.2, Appendix 2.

### **8.5.1. Time Period and Frequency for Collecting AE, TEAE, SAE, and TESAE Information**

Medical occurrences that begin before the start of study intervention and not related to required study procedures, but after obtaining informed consent will be recorded on the Medical History/Current Medical Conditions section of the case report form (CRF) and not as AEs.

All medical occurrences will be considered AEs/SAEs if identified during the screening period and are related to study-required procedures or interventions and will be collected starting after completion of the informed consent process to Day 0 prior to randomization.

All TEAEs and treatment-emergent SAEs (TESAEs) will be collected after study drug administration on Day 0 through Day 180 (see definition of TEAE, Section 10.2).

All SAEs, including TESAEs, will be recorded and reported to the Sponsor or designee immediately and under no circumstance should this exceed 24 hours, as indicated in Section 10.2.5, Appendix 2. The Investigator will submit any updated SAE/TESAE data to the Sponsor within 24 hours of its availability.

Investigators are not obligated to actively seek AEs or SAEs after conclusion of the study participation. However, if the Investigator learns of any SAE, including a death, at any time after a Participant has been discharged from the study, and he/she considers the event to be possibly, probably, or definitely related to the study intervention or study participation, the Investigator must promptly notify the Sponsor.

### **8.5.2. Method of Reporting AEs, TEAEs, SAEs, TESAEs, and AESIs**

The method of recording, evaluating, and assessing causality of AEs, SAEs, TEAEs, TESAEs, and AESIs and the procedures for completing and transmitting SAE reports are provided in Section 10.2, Appendix 2.

Care will be taken not to introduce bias when identifying AEs/TEAEs and/or SAEs/TESAEs. Open-ended and non-leading verbal questioning of the Participant is the preferred method to inquire about AE occurrences.

### **8.5.3. SAE Reporting to the Sponsor or Designee**

All SAEs/TESAEs should be reported to the Sponsor or designee within 24 hours of knowledge of the SAE/TESAE occurring.

## 8.5.4. Adverse Events of Special Interest

### Categories of AESIs

There are four main categories of AESIs: 1) those considered to be related to the angiogenesis potential of Engensis, 2) other medical problems in this patient population, 3) severe (Grade 3) and potentially life-threatening (Grade 4) Injection Site Reactions, and 4) COVID-19 infections occurring after randomization of the participants. The Sponsor is responsible for deciding which events are deemed as AESIs

#### 8.5.4.1. AESIs Related to Angiogenesis

##### Atherosclerosis

Hyperplasia of the vasa vasorum in the early stages of atherosclerosis is independent of angiogenesis, but the intimal neovascularization that follows the hyperplasia of the vasa vasorum is angiogenesis-dependent. Angiogenesis increases oxygen and nutrients to the artery wall and supports initial plaque growth. Once the atherosclerotic plaque develops, intimal angiogenesis is thought to contribute to characteristics of an unstable plaque, plaque hemorrhage, and plaque rupture. Therefore, diagnoses suggestive of recent coronary artery disease since Baseline will be evaluated as AESIs.

##### Proliferative diabetic retinopathy

Neovascularization is an advanced stage of diabetic retinopathy that is due to relentless abnormal fibrovascular proliferation. Because the angiogenic potential of Engensis may promote the development of or stimulate abnormal fibrovascular proliferation in the retina, new fundoscopic changes or symptoms of proliferative diabetic retinopathy that occur after Baseline are considered AESIs.

##### Cancer

Angiogenesis plays an important role in the proliferation and metastatic spread of cancer as these processes are dependent on an adequate supply of oxygen and nutrients and removal of waste products. All types of cancer reported after randomization will be deemed to be AESIs.

Diabetes mellitus and obesity (BMI  $\geq 30$ ) each increases the risk of several types of cancer. In type 2 DM, there is a 2- to 3-fold increased risk for pancreatic cancer, a 2-fold increased risk for hepatobiliary and endometrial cancers, a 50% increased incidence of colorectal cancer, and a 20% increased risk for breast cancer. Obese postmenopausal women have an increased risk of breast cancer, and obesity is associated with a modestly increased risk of colorectal cancer, pancreatic cancer, and prostate cancer.

Because the medical problems of type 2 DM and obesity (BMI  $\geq 30$ ) increase the risks of several types of cancers, cancer screening tests have been implemented to exclude obese diabetic patients with even higher than expected risks of developing cancer based on medical history or cancer screening tests, or who have various types of subclinical cancer.

#### 8.5.4.2. AESIs Related to Other Medical Problems

Several medical problems are frequently observed in patients with diabetic peripheral neuropathy

that should be considered AESIs. These medical problems are listed below by type of medical problem.

#### Infections and infestations; Skin and Subcutaneous disorders

Because patients with diabetic peripheral neuropathy are at an increased risk to develop skin lesions (e.g., blisters, ulcers) and various lower limb infectious complications (e.g., cellulitis, osteomyelitis) that may be associated with systemic infections (e.g., bacteremia, sepsis, or septic shock), all of these types of medical problems that occur after Randomization (Day 0) will be considered AESIs. In addition, any amputations involving the lower extremity, development of Charcot foot, or other similar complications will also be considered AESIs.

#### Peripheral Arterial Disease

An overlap of DPN and peripheral arterial disease (PAD) apparently exists in type 2 diabetic patients. Because Participants with DPN may develop signs or symptoms of PAD after randomization in the VMDN-003-2 trial, detailed evaluations of Participants considered to have PAD will be considered AESIs.

#### Diabetic Neuropathies

Because Participants in this study may develop other types of peripheral diabetic neuropathies while in the study, the following events will be considered to be AESIs in Participants with DPN: diabetic mononeuropathy, diabetic mononeuropathy multiplex, and diabetic polyradiculopathy. The occurrence of these other types of peripheral neuropathies in a Participant with DPN may indicate a more severe form of diabetic peripheral neuropathy.

Because Participants in this study may develop various manifestations of autonomic neuropathy (typically involves the gastrointestinal, genitourinary tract, cardiovascular systems) after randomization, the clinical manifestations of diabetic autonomic neuropathy will be considered to be AESIs.

#### Glycemic Control

Hypoglycemia, hyperglycemia, hyperlipidemia, hypercholesterolemia, and hypertriglyceridemia are to be listed as AESIs based on the Common Terminology Criteria for Adverse Events (CTCAE) grading if they are Grades 3 or 4.

Metabolic complications of DM (such as diabetic ketoacidosis [DKA], hyperglycemic hyperosmolar non-ketotic coma, lactic acidosis, metabolic acidosis [overlaps with DKA]) are to be listed as AESIs.

### **8.5.4.3. Injection Site Reactions**

Immediately following completion of injections of Engensis or Placebo at each Study Injection Visit (on Days 0, 14, 90, and 104), the Investigator or designee must evaluate all injection sites for any reactions and record the findings on the Injection Site Reaction (ISR) CRF. Within 2 to 3 days after each Study Injection Visit, a documented telephone call will be placed from the clinical site to the Participant to ask if there are any Injection Site Reactions (across all injection sites on both calves), and if any ISRs occurred, the worst reaction across all injection sites is to be reported as a TEAE and will be considered an AESI if severe (Grade 3) or potentially life-threatening (Grade 4). Grading of severity of ISRs is presented in Section 10.3, Appendix 3.

For an ISR to qualify as an AESI, the severity of the ISR should be Grade 3 or 4 according to the grading presented in Table 6. Injection Site Reactions that are observed by the PI or reported by the participant within 2 to 3 days after Study Injections on Days 0, 14, 90, and 104. The PI should conduct an unscheduled visit, if warranted, to assess the ISR. The ISRs that remain unresolved after 2 to 3 days will continue to be assessed at subsequent Visits as ongoing AEs until resolved.

#### **8.5.4.4. COVID-19 Infections**

A diagnosis of a COVID-19 infection occurring in participants after randomization will be recorded as an AESI and their disposition during the trial following the diagnosis of the COVID-19 infection will be tracked.

#### **8.5.5. Follow-up of AEs/TEAEs, SAEs/TEAEs, and AESIs**

After the initial AE/TEAE/SAE/TEAE report, the Investigator is required to proactively follow each Participant at subsequent Visits/contacts. All SAEs and AESIs (see Section 8.5.4) will be followed until resolution, stabilization, the event is otherwise explained, or the Participant is lost to follow-up (as defined in Section 7.3).

#### **8.5.6. Regulatory Reporting Requirements for SAEs/TEAEs**

Prompt notification by the Investigator to the Sponsor of an SAE/TEAE is essential to ensure that legal obligations and ethical responsibilities towards the safety of Participants and the safety of a study drug under clinical investigation are met.

The Sponsor has a legal responsibility to notify both the local regulatory authority and other regulatory agencies about the safety of a study drug under clinical investigation. The Sponsor will comply with country-specific regulatory requirements relating to safety reporting to the regulatory authority, Institutional Review Boards (IRBs), and Investigators.

For all studies, Investigator Safety Reports must be prepared for suspected unexpected serious adverse reactions (SUSARs) according to local regulatory requirements and Sponsor policy and forwarded to Investigators as necessary.

An Investigator who receives an Investigator Safety Report describing an SAE or other specific safety information (e.g., summary or listing of SAEs) from the Sponsor will review and then notify the IRB if appropriate according to local requirements.

##### **8.5.6.1. Sponsor's Responsibility**

All AEs and SAEs will be reported on an annual basis to FDA in accordance with the IND regulation (21 CFR 312). Per the 2010 FDA Guidance Document for Industry and Investigators "Safety Reporting Requirements for INDs and BA/BE Studies," events categorized as "possibly" or "probably" related will be treated as "suspected adverse reactions." Events categorized as "definitely" related will be treated as an "adverse reaction."

All serious and unexpected study-drug-related or suspected adverse reactions will be reported to FDA and to all participating Investigators as an IND Safety Report within 15 calendar days of

the event after the Sponsor determines that the suspected adverse reaction qualifies for reporting (21 CFR 312.32). Any unexpected fatal or life-threatening, study-drug-related, or suspected adverse reaction will be reported to the Agency within 7 calendar days after the Sponsor's initial receipt of the information.

The Sponsor will notify all participating Investigators of any new safety information that alters the current risk-benefit assessment of the study medication or that would be sufficient to consider changes in Engensis administration or in the overall conduct of the study.

### **8.5.7. Pregnancy and Contraception**

#### **8.5.7.1. Pregnancy Test (Women of Childbearing Potential Only) and Contraception**

Female Participants must be nonpregnant, nonlactating, and either postmenopausal for at least 1 year, or surgically sterile for at least 3 months, or agree to use double-barrier contraception from 28 days prior to randomization and/or their last confirmed menstrual period prior to study randomization (whichever is longer) until 2 months after study completion. Male Participants must also agree to use double-barrier contraception from randomization until 2 months after study completion.

Double-barrier female contraception may include, but is not limited to, intrauterine device with spermicide, female condom with spermicide, diaphragm with spermicide, cervical cap with spermicide.

For women of childbearing potential, a urine beta human chorionic gonadotropin ( $\beta$ -HCG) test will be performed during Screening and before randomization (Day 0); results of the test must be negative. The  $\beta$ -HCG test will also be performed at Day 180 or the last Study Visit to evaluate whether the Participant is pregnant.

The rhythm method and contraception by a partner are not considered acceptable methods of contraception.

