All Participants will receive sixteen (16) 0.5-mL IM injections of Engensis or Placebo in each calf gastrocnemius muscle at each of two Visits during two Treatment Cycles: Treatment Cycle 1 on Day 0 and Day 14, and Treatment Cycle 2 on Day 90 and Day 104. At 2 hours ( $\pm$  1 hour) after completion of IM injections of Engensis or Placebo on Days 0 and 14 and Days 90 and 104, vital signs and blood draw for cytokine levels will be performed.

Treatment-emergent adverse event (TEAE) assessment, including injection site reactions, will start as of randomization (Day 0) and continue throughout the study.

Follow-up Study Visits will be conducted on Days 28, 60, 150, and 180 or early termination (ET). Vital signs will be recorded at all Study Visits. At the Day 180 Visit (end of study), the following assessments will be conducted: the full BPI-DPN (performed for 7 days prior to the Day 180 Visit), MNSI, BST, Patient Global Impression of Change (PGIC), and the quality of life assessments (36-item Short Form Health Survey [SF-36] and EuroQol Health Utilities Index [EQ-5D]), urine drug analysis, urine pregnancy status (females only), retinal funduscopy, physical examination, concomitant medications and procedures, and anti-HGF antibodies. Blood will be drawn for determination of serum chemistry, lipid profile, hematology, and HbA1c levels.

The purpose of this study is to assess the efficacy and safety of Engensis compared to Placebo as measured by changes in the means of the Average Daily Pain Scores (ADPSs) of the BPI-DPN, selected blood cytokines, BST, and assessments of injection site reactions, physical examination, laboratory assessments, vital signs, TEAEs, and treatment-emergent serious adverse events (TESAEs).

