## **5. STUDY POPULATION**

### **5.1. Inclusion Criteria**

1. Male or female Participants age  $\geq 18$  years at time of completion of the informed consent process
2. Type 1 or 2 diabetes mellitus (DM) and on current Standards of Medical Care in Diabetes – 2020 optimal guideline-directed medical therapy in Participants (including vaccine recommendations if possible), AND without unstable diabetes or significant medical problems, such as progressive end-organ disease, within 3 months of or during Screening, in the judgment of the Investigator
3. Glycosylated hemoglobin A1c (HbA1c) of  $\leq 10.0\%$  using the first assessment collected during Screening
4. Documented diagnosis of bilateral painful DPN in both lower extremities at least 6 months prior to Screening
5. An ADPS  $\geq 4$  (standard deviation  $\geq 0.3$  and  $\leq 1.5$ ) that is completed during the 7 days prior to randomization (Day 0)
6. The physical examination component of the Michigan Neuropathy Screening Instrument (MNSI) score of  $\geq 2.5$
7. If on medication for painful DPN (other than gabapentin or pregabalin), must be on a stable dose defined as  $< 50\%$  change in total dose over 3 months prior to completion of informed consent
8. Male Participants and their female partners must agree to use double-barrier contraception during the study or provide proof of postmenopausal state (minimum 1 year) or surgical sterility
9. Male Participants must not donate sperm during the study
10. Female Participants must be nonpregnant, nonlactating, and either postmenopausal for at least 1 year, or surgically sterile for at least 3 months, or agree to use double-barrier contraception from 28 days prior to randomization and/or their last confirmed menstrual period prior to study randomization (whichever is longer) until the end of the study
11. Capable and willing to comply with the requirements and restrictions of the protocol and informed consent form
12. Able to complete all screening activities within 52 days of signing the informed consent form

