## 8. STUDY ASSESSMENTS AND PROCEDURES

Study procedures and their timing are summarized in Section 1.3 (SoA).

Protocol waivers or exemptions are not allowed. Adherence to the protocol requirements, including those specified in the SoA, is essential.

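### Inclusion criteria 8 and 10 omit the two-month post-study contraception period that Protocol Section 8.5.7.1 requires of women and men

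*Protocol*

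**What the plan says.** Section 8.5.7.1 of the Protocol sets the contraception period for both sexes. For women who are neither postmenopausal nor surgically sterile, it starts 28 days before randomization or at the last confirmed menstrual period and ends with "whichever is longer) until 2 months after study completion". For men: "Male Participants must also agree to use double-barrier contraception from randomization until 2 months after study completion".

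Section 5.1 covers the same ground in two inclusion criteria. Criterion 10 gives women the same start but ends with "whichever is longer) until the end of the study". Criterion 8 reads "Male Participants and their female partners must agree to use double-barrier contraception during the study", with an alternative: "or provide proof of postmenopausal state (minimum 1 year) or surgical sterility". Neither criterion mentions a post-study period or refers to Section 8.5.7.1.

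Two general provisions bear on the point. Criterion 11 requires that the participant be "Capable and willing to comply with the requirements and restrictions of the protocol and informed consent form". Section 8 adds: "Protocol waivers or exemptions are not allowed".

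The end-point terms are used at two levels:

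- **Participant level.** The synopsis (Overall Design) says "At the Day 180 Visit (end of study), the following assessments will be conducted". The Day 180 column of the Schedule of Activities is headed as end of study or early termination. Section 4.7 treats a participant as complete at the Day 180 Visit, given enough diary entries.
- **Trial level.** Section 4.5 puts the end of the study at the last participant's Day 180 Visit or discontinuation. Section 4.6 treats the study as complete only once the sponsor has approved the clinical study report.

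**The concern.** Criterion 10 and the sentence on women in Section 8.5.7.1 are nearly the same text with different endings, and the rule for men differs in the same way. A rule meant to protect participants and any pregnancy therefore has two end dates.

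The criteria are what a site works through when it takes a participant's agreement. They are also what the Adjudication Committee checks before randomization (Section 5.4.1). A site could follow criteria 8 and 10 exactly and record agreement to the shorter period.

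During the extra two months, that agreement is the main safeguard the Protocol describes. The last pregnancy test is at Day 180 or the last study visit (Section 8.5.7.1). Pregnancy information is collected on women who conceive while they are taking part, and investigators need not actively look for pregnancy-related serious events afterwards (Section 8.5.7.2).

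**Working it through.** There is no planned figure to reproduce. The check compares the texts and then counts days under each reading of the end-point terms.

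**Text comparison**

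| | Section 5.1 | Section 8.5.7.1 |
|---|---|---|
| Women, start | 28 days before randomization or last menstrual period | Same |
| Women, end | End of the study (criterion 10) | Two months after study completion |
| Men, start | Not stated beyond the study itself (criterion 8) | Randomization |
| Men, end | The study itself (criterion 8) | Two months after study completion |

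Both columns are current text. Neither is redacted or taken from the amendment history.

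**Participant-level reading, nominal schedule**

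Inputs: last injection on Day 104 and final visit on Day 180 (Schedule of Activities). Assumption: two months is taken as 60 days (calendar range 59 to 62).

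- Under the criteria: 180 − 104 = 76 days after the last injection.
- Under Section 8.5.7.1: 180 + 60 = Day 240, and 240 − 104 = 136 days.
- Gap: 136 − 76 = 60 days.

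**Participant-level reading, visit windows**

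Inputs: Day 90 ± 7, the Day 104 Visit 13 to 15 days after the Day 90 Visit, Day 180 ± 7.

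- Day 104 Visit: earliest 83 + 13 = Day 96, latest 97 + 15 = Day 112.
- Day 180 Visit: Day 173 to Day 187.
- Under the criteria: 173 − 112 = 61 to 187 − 96 = 91 days.
- Under Section 8.5.7.1: 61 + 60 = 121 to 91 + 60 = 151 days.

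These ranges leave out two allowances that could widen them slightly: rescheduling the Day 180 Visit by up to 3 days (Schedule of Activities, footnote 24) and completing interrupted injections within 48 hours (Section 6.6). Neither changes the gap, because both end dates are counted from the same final visit.

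**Other readings**

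- **Both terms at trial level (Sections 4.5 and 4.6).** Criterion 10 ends at the last participant's final visit. Section 8.5.7.1 ends two months after approval of the study report, which comes later than that visit. The gap is two months plus an interval the documents do not give.
- **End of study at trial level, completion at participant level.** For someone enrolled early, criterion 10 could outlast Section 8.5.7.1, since the last participant's Day 180 Visit may fall after that person's own Day 240. This mixes two levels for closely related terms and is a strained reading. The two texts would still disagree.

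No natural reading makes the two sections agree.

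**The case against.** The strongest answer is that the two rules are compatible. Anyone who follows Section 8.5.7.1 also meets criteria 8 and 10 on the natural readings. Criterion 11 makes willingness to follow the whole Protocol a condition of entry, and waivers are barred. The definitions in Section 10.5.2 also send the reader to Section 8.5.7 for contraception. On this view the criteria set a minimum and the later section adds to it.

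Much of that stands, and it is why the point is minor. It does not remove the mismatch. Neither criterion 11 nor the no-waiver rule tells a site which end date to obtain agreement to. The definitions entry concerns the method of contraception, under a term that criteria 8 and 10 do not use.

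A second objection is that no harm is shown. That also stands. A reader might infer that participants will be left unprotected, or that stopping at Day 180 is unsafe. The documents do not support either inference. The consent form was not available and may already state the longer period. Nothing shows that any site would record the shorter one. Section 2.2.6 reports no sign of genomic integration or potential germ cell transmission in animals. The reviewed text gives no duration of expression from which to judge 76 days inadequate. The argument for alignment is only that the two-month period is the sponsor's own requirement.

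**Conclusion.** The inconsistency is real and holds for both sexes: criteria 8 and 10 leave out a two-month period that Section 8.5.7.1 requires. It is a minor participant-safety matter with no bearing on power, alpha or the efficacy analysis.

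A reader might take 60 days as the established size of the gap. It is so only if both end points mean the participant's own Day 180 Visit and two months is counted as 60 days. The synopsis, the Schedule of Activities and Section 4.7 make that the natural reading, but the formal definitions in Sections 4.5 and 4.6 are at trial level. On those definitions the documents support only a gap of at least two months.

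Confidence is high that the texts differ. It is lower on the practical consequence, which depends on the unseen consent form and on what sites actually record.

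**What to change.** Amend criteria 8 and 10 so that the contraception period runs to two months after study completion, as in Section 8.5.7.1. In both criteria and in Section 8.5.7.1, state that completion here means the participant's own completion or end of participation, not the report approval of Section 4.6. Then check that the consent form gives the same end date.

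Two further changes may suggest themselves, but should not be made part of this correction:

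- **A fixed anchor for early terminators.** Counting from the early-termination visit gives someone who leaves on an injection day 0 + 60 = 60 days of cover. Counting from the scheduled Day 180 gives someone last injected on Day 14 a period of 240 − 14 = 226 days, against 136 for a completer. The documents give no basis for preferring either, so the sponsor should decide and state the choice.
- **Copying criterion 8's exemption into the sentence on men in Section 8.5.7.1.** The postmenopausal part can apply only to female partners, and that sentence names only male participants.

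The cost is a short wording change in Sections 5.1 and 8.5.7.1, and in the consent form if it does not already match. The eligibility criteria will state a slightly longer commitment, but Section 8.5.7.1 already requires it. Visits, sample size and analyses do not change.
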